2.10.2 Concomitant medication

Participants will be asked to identify any medications they are taking at baseline and any changes in medication will be recorded across the trial, i.e., at each follow-up time point (eight weeks and 6 months) thereafter.

2.11 Co-enrolment into other trials

Participants in this trial may be eligible for co-enrolment in other studies, and this will be decided on a case-by-case basis by the Chief Investigator and TMG of iRehab and any respective studies. The WCTU trial office should be informed if co-enrolment is being considered. Any co-enrolment agreements records retained by WCTU and details of co-enrolment should be documented in the CRF.

2.12 End of trial

The trial will end when all participants have completed their six-month follow-up and related trial activities have been completed.

The trial will be stopped prematurely if:

- Mandated by the Ethics Committee
- Recommended by the DMC

- Funding for the trial ceases

The Research Ethics Committee will be notified in writing within 90 days when the trial has been concluded or within 15 days if terminated early.

3. METHODS AND ASSESSMENTS

3.1 Schedule of delivery of intervention and data collection

An overview of schedule of trial assessments is given in Table 3.

Table 3 – Schedule of delivery of data collection

	Pre-randomisation		Post-randomisation			
	Screening	Baseline	Intervention	Follow-up		
Weeks ± No. Days	Weeks 0-12		Weeks 1-6	Week 8	8-26 weeks	Week 26
Check eligibility	✓	✓				
Consent participant		✓				
Clinical data collection (by site)						
APACHE II score		✓				
Medical history		✓				
Co-morbidities		✓				
Pre-ICU admission functional status		✓				
Duration ventilation		✓				
Length of ICU stay		✓				
Length hospital stay		✓				
Participant data collection						
EQ-5D-5L		✓		✓		✓
30sec Sit-to-Stand		✓		✓		✓
BIPQ		✓		✓		✓
FACT-F		✓		✓		✓
HADS		✓		✓		✓
Health and social care use				✓		✓
TFAQ				✓		
Randomisation		R*				
Intervention delivery			✓			
Process evaluation						

	Pre-randomisation		Post-randomisation			
	Screening	Baseline	Intervention	Follow-up		
Weeks ± No. Days	Weeks 0-12		Weeks 1-6	Week 8	8-26 weeks	Week 26
					✓	
Participant self-report/Site data collection						
AEs		✓	✓	✓		✓
SAEs		✓	✓	✓		✓

*Randomisation after consent and participant baseline data collection. Refer to outcome section for questionnaire measures.

4. ETHICAL CONSIDERATIONS

The trial will be conducted in conformance with the principles of the Declaration of Helsinki and to Good Clinical Practice (GCP) guidelines. It will also comply with all applicable UK legislation and Warwick Standard Operating Procedures (SOPs). All data will be stored securely and held in accordance with the UK GDPR and Common Law Duty of Confidentiality.

Ethical approval will be sought using the Integrated Research Application System prior to commencing this trial. Sites will only be permitted to enrol patients into the trial once all required agreements are in place. Key ethical issues that we have considered for this trial relate to (i) eligibility and access to underserved groups, and (ii) information governance relating to the remote intervention delivery.

As discussed in Section 2.3, the trial has broad inclusion criteria to ensure the trial offered to all patients post-ICU that might benefit from rehabilitation. We will review characteristics of those recruited and compare these to the overall population of adults in ICU. We will develop strategies to address invitation bias.

The iRehab trial uses remote consent and delivery of the rehabilitation intervention, including prescription and delivery of exercise, as well storage of personal data. We will ensure that the trial information governance strategy is developed including risk assessments that optimise patient safety for remote delivery (68-70).

5. ADVERSE EVENT MANAGEMENT

5.1 Definitions

5.1.1 Adverse Events (AE)

An Adverse Event (AE) is defined as any untoward medical occurrence in a clinical trial participant which does not necessarily have a causal relationship with the treatment/intervention.

AEs exempt from recording

These are common AEs associated with exercise and will not be recorded as AEs for this trial (Table 4)

Table 4 – Common AEs associated with exercise

Events
Breathlessness
Light headedness/dizziness
Muscle stiffness/soreness
Tiredness/fatigue
Oxygen desaturation (that resolves with appropriate management e.g. rest, breathing exercises, inhaled medications)

For the **intervention group**, AEs listed in Table 4 that are identified during or after the intervention, will be recorded on the intervention notes (not on an AE form), for clinical purposes only. For all participants, AEs listed in Table 4 identified during outcome assessment will be recorded on the iRehab database.

Any AEs that are not listed in Table 4 should be recorded using the Adverse Event eCRF. Recording should be done by the intervention team, outcome assessor or investigator site, as appropriate, within 48 hours of becoming aware of the AE. All AEs should be assessed to see if they constitute a 'Serious' adverse event as per section 5.1.2 below. If they do, they will be reported by the mechanism in section 5 and not recorded on the AE form.

5.1.2 Serious Adverse Events (SAEs)

A Serious Adverse Event is an AE that fulfils one or more of the following criteria:

- Results in death
- Is immediately life-threatening
- Requires hospitalisation or prolongation of existing hospitalisation
- Results in persistent or significant disability or incapacity
- Is a congenital abnormality or birth defect
- Is an important medical condition or Immediate intervention was required to prevent one of the above

SAEs exempt from reporting

The following SAEs listed in Table 5 are common in the clinical population being studied and **do not** require reporting to the Clinical Trials Unit as an SAE for this trial, but will be recorded as part of follow-up data collection in the participant questionnaires or in the relevant section(s) of the CRF (such as the hospital readmission CRF):

Table 5 – Common SAEs in the clinical population being studied that are exempt from reporting

Events
Hospitalisation, or death, for pre-existing conditions e.g. respiratory exacerbation and infection, or a complication related to the initial ICU admission
Treatment, which was elective or pre-planned, for a pre-existing condition, not associated with any deterioration in condition

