1. BACKGROUND

1.1 Epidemiology and burden of the condition

The UK Intensive Care National Audit and Research Centre, described approximately 172,000 admissions to critical care units in England, Wales, and Northern Ireland, with approximately 129,000 patients surviving critical illness discharged from acute hospitals over one year (April 2019 to March 2020) (1). The consequences of critical illness are substantial and multifactorial, and often encompass physical deconditioning, respiratory and swallowing problems, reduced activities of daily living, cognitive and mental health impairments, fatigue, and declines in health-related quality of life (HRQoL) (2-8). In the UK, one in four people recovering from critical illness experience an unplanned hospital readmission within 90 days of discharge, substantially higher rates of readmission than hospitalised patients without an ICU stay (9). At a societal level, nearly half of ICU survivors fail to return to work after 12 months, (10-11) with UK data highlighting the increase in social care support required (11). Therefore there is a need to intervene to improve the long term health of patients discharged home after intensive care. Identifying ways to support people returning home after a stay in ICU has been ranked a key priority for research by patients, their families, and researchers (12).

Guidance has recommended remote rehabilitation as standard of care for critically ill survivors following COVID-19 (13,14). There is no evidence to support the delivery of remote rehabilitation to the broader population of survivors of critical illness, despite its use and anecdotal evidence of acceptability across many disease populations. This trial will provide evidence on whether remote rehabilitation is clinically and cost-effective for survivors following critical illness post-ICU care. This trial will provide high quality evidence regarding the effectiveness of remote rehabilitation on health-related outcomes and whether rehabilitation should be implemented more widely across the NHS or withdrawn if there is no evidence of improved outcomes for patients.

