5.2 Assessing and Reporting AEs, SAEs and related SAEs

5.2.1 Recording and assessing AEs/SAEs

All **AEs** and **SAEs** (unless otherwise specified) occurring from the time of **informed consent** until 8 weeks post randomisation and during the 8 week and 6-month outcome assessment appointments, must be recorded (AE)/reported (SAE) (where events are usually within 48 hours of the assessment appointment).

During the baseline, eight- week or six-month assessment all participants will be asked about anything that might constitute an AE or SAE by the independent assessor performing the assessment. AEs/SAEs occurring during the intervention delivery in the intervention group will be determined through patient report at each weekly online catch-up session.

All SAEs, except for those listed in Table 5, should be initially reported by the site, the outcome assessor or a member of the intervention delivery team, as appropriate. A copy of the SAE form should be sent to the WCTU trial team via the trial database and the WCTU QA Team will be notified by the WCTU trial team. WCTU should be informed **within 24 hours** of any party becoming aware of the event.

Once received, the trial management team at WCTU will review the SAE. Information will be requested from the recruiting site to provide further detail on the SAE if required. If the patient was treated for the SAE at the investigator site that recruited the patient, WCTU will send the SAE on to the investigator site for completion within 2 working days (if not already reported by the site). If not then WCTU will contact the patient or the patients GP for further information where applicable.

For each **SAE** the following information will be collected from the intervention team, assessor and/or investigator site (as appropriate):

- details in medical terms and case description
- event duration (start and end dates, if applicable)
- action taken
- outcome

- seriousness criteria
- causality (i.e. relatedness to intervention), in the opinion of the investigator

The causality of SAEs (i.e. relationship to trial treatment) will be assessed by the site Principal Investigator and Chief Investigator(s) on the SAE form using Table 6.

Table 6 – SAE causal relationships

Relationship to trial intervention	Description
Unrelated	There is no evidence of any causal relationship

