5.6 Notification of deaths

All deaths will be reported to the sponsor (Ulster University) and WCTU irrespective of whether the death is related to disease progression, the intervention, or an unrelated event. These should be reported within 24 hours of a staff member becoming aware of the event to WCTU using the eCRF.

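### Table 5 exempts serious events put down to pre-existing illness or the ICU stay from SAE reporting, with no exception for events possibly related to the intervention or an outcome assessment

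*Protocol*

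**What the plan says.** Table 5 in Protocol section 5.1.2 lists two kinds of serious event that are common in this population and exempt from SAE reporting. The first row is "Hospitalisation, or death, for pre-existing conditions e.g. respiratory exacerbation and infection, or a complication related to the initial ICU admission". The second is elective or pre-planned treatment for a pre-existing condition, and it carries a limit: "not associated with any deterioration in condition". The first row has no limit of any kind.

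The lead-in says that these events do not "require reporting to the Clinical Trials Unit as an SAE for this trial, but will be recorded as part of follow-up data collection"; it names the hospital readmission CRF as one place for this. Section 5.2.1 carries the exemption into the reporting rule: "All SAEs, except for those listed in Table 5, should be initially reported by the site" or by the outcome assessor or intervention team.

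For SAEs that are reported, section 5.2.1 says that causality "will be assessed by the site Principal Investigator and Chief Investigator(s) on the SAE form using Table 6". Under section 5.2.4 the Chief Investigator's independent assessment follows completion of that form. Events judged at least possibly related to the intervention or an outcome assessment go to the ethics committee and sponsor within 15 days, to the oversight committees at their next meetings, and to the other sites. Section 5.2.3 adds that no SAEs are expected for this intervention, so any related one is expedited automatically.

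Two other sections capture some of the exempt events. Section 5.5 has sites report every readmission by eCRF. Section 5.6 has every death reported to the sponsor and the trials unit within 24 hours, "irrespective of whether the death is related to disease progression, the intervention, or an unrelated event".

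**The concern.** The exemption is decided by the underlying condition alone. The question of whether the intervention contributed is asked only on a form that an exempt event does not need. Exercise is prescribed remotely to people in whom section 2.10.1 anticipates high comorbidity, so a pre-existing respiratory or other condition could worsen soon after a session. If that leads to admission or death, the plan as written allows it to be filed as background illness before anyone rates relatedness.

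Two things are at stake. An event that the protocol's own scale would call possibly related could go without expedited notification. And SAEs are the trial's stated safety outcome (Trial Summary; section 2.2.2), so such an event would be missing from the SAE data given to the committees, although it remains in the database under another heading.

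**Working it through.** No arithmetic applies; the check is to follow one event through the sections.

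Take a participant with a pre-existing respiratory condition who has an exacerbation soon after an exercise session and is admitted.

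1. **Is it serious?** Yes. Hospitalisation is a seriousness criterion in section 5.1.2.
2. **Is it exempt?** Yes. It falls in the first row of Table 5, which has no condition on timing or relatedness. The limit in the second row applies to elective treatment only.
3. **Is an SAE form required?** No, under sections 5.1.2 and 5.2.1.
4. **How would Table 6 rate it?** The category for a possible relationship describes an event that follows the intervention within a reasonable time and to which the participant's clinical condition may also have contributed. The event fits. Coexisting illness is part of that category, not a reason to leave it.
5. **What would that rating trigger?** Under sections 5.2.3 and 5.2.4: ethics committee and sponsor notification within 15 days, committee reporting, and notice to other sites.
6. **Does the rating get made?** No step requires it. The Table 6 rating is made on the SAE form, and the Chief Investigator's review follows that form.

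Steps 3 and 5 cannot both operate for this event. The remaining safety text does not close the gap:

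| Section | What it adds | What it leaves open |
|---|---|---|
| 5.2.2 | Related SAEs are reported under the trials unit's own procedure | Applies once an SAE has been assessed as related |
| 5.4, assessor and intervention team | Clinical judgement on seriousness and causality of AEs; every SAE to the trials unit within 24 hours | Does not mention Table 5, so it contradicts the exemption without overriding it |
| 5.5 | All readmissions captured; SAE status decided with the help of the readmission date | Relatedness is not mentioned, nor is precedence over Table 5 |
| 5.6 | All deaths notified within 24 hours | No causality step described |
| 6.1 | Death notification form from the recruiting site | No causality item described |

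The same tracing for a fall, an exercise injury or a condition not attributed to earlier illness or the ICU stay gives a different result: none is in Table 5, so each needs an SAE form within 24 hours and reaches Table 6.

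**The case against.** The best defence is that nothing is lost. Exempting common background events is ordinary practice in a population with heavy morbidity. Exempt events are still recorded, all readmissions and deaths reach the trials unit, section 5.5 gives each readmission a second look, section 5.4 asks the people closest to the event to judge causality, and the DMC reviews unblinded overall safety data. This stands as regards capture: the data exist. It does not stand as regards causality. None of these steps requires relatedness to be rated for a Table 5 event, and a general duty of judgement in section 5.4 does not displace the explicit exception in section 5.2.1.

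Four stronger readings are tempting and not supported.

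- **That Table 5 contradicts the all-deaths rule.** Table 5 waives reporting as an SAE; section 5.6 is a separate notification. Both can be followed. Routes and timing are poorly aligned, but that is all.
- **That exercise-related serious events in general escape review.** Only those classed as pre-existing or ICU-related do.
- **That the scale can be read from section 1.1**, which says that "one in four people recovering from critical illness experience an unplanned hospital readmission within 90 days of discharge". A reader might compute 0.25 × 231 = 57.75, about 58 in the intervention arm, or 0.25 × 428 = 107 overall. That rate is for all-cause unplanned readmission in critical illness survivors generally. Consent may come up to 12 × 7 = 84 days after discharge, leaving as little as 90 − 84 = 6 days of the window, before baseline assessment and randomisation. The 107 also includes controls, who do not receive the intervention. Neither figure estimates exempt events or related ones.
- **That 48 hours is the plan's attribution window.** In Table 6 it is only an example, in the row for unlikely relationships.

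Tabulation of readmissions and deaths by arm belongs to the SAP, which is not shown, so its absence is no fault here.

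**Conclusion.** The concern holds in a bounded form. For hospitalisation or death attributed to a pre-existing condition or an ICU-related complication, the protocol provides no required route to causality assessment, and so none to expedited reporting, even where the event would meet its own definition of a possible relationship. The assertion in section 5.2.3 that any related SAE is automatically expedited is therefore not secured for this class. There is also a plain inconsistency between section 5.4, which sends every SAE to the trials unit within 24 hours, and sections 5.1.2 and 5.2.1, which except Table 5.

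No number of affected events can be derived from the documents. The conclusion assumes that staff apply Table 5 as written, and that the readmission and death forms contain no relatedness item; the protocol describes none, but the forms themselves are not shown. If they do contain one, the remaining fault is that the protocol does not say so or link it to section 5.2.4.

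**What to change.** 1. State in Table 5 and in section 5.2.1 that the exemption does not apply to any event that the site, the outcome assessor, the intervention team or the Chief Investigator considers possibly related, or rated higher on Table 6, to the intervention or to an outcome assessment.
2. Add a relatedness item to the readmission CRF and the death notification, so that the question is asked for every exempt event and a positive answer opens an SAE form. Section 2.6.1 already has the recruiting site's research team informed of randomisation, so a site-completed item need not reveal allocation to the blinded assessor.
3. Reconcile sections 5.1.2, 5.2.1, 5.4, 5.5 and 5.6: whether the 24-hour duty in 5.4 is subject to Table 5, whether a decision under 5.5 overrides Table 5, and how a death notified under 5.6 receives a causality assessment.

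The cost is a wording amendment, one added item on two forms, and a modest number of additional SAE forms. Background events judged unrelated or unlikely to be related stay exempt, so the purpose of Table 5 is kept.

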5.2 Assessing and Reporting AEs, SAEs and related SAEs

5.2.1 Recording and assessing AEs/SAEs

All **AEs** and **SAEs** (unless otherwise specified) occurring from the time of **informed consent** until 8 weeks post randomisation and during the 8 week and 6-month outcome assessment appointments, must be recorded (AE)/reported (SAE) (where events are usually within 48 hours of the assessment appointment).

During the baseline, eight- week or six-month assessment all participants will be asked about anything that might constitute an AE or SAE by the independent assessor performing the assessment. AEs/SAEs occurring during the intervention delivery in the intervention group will be determined through patient report at each weekly online catch-up session.

All SAEs, except for those listed in Table 5, should be initially reported by the site, the outcome assessor or a member of the intervention delivery team, as appropriate. A copy of the SAE form should be sent to the WCTU trial team via the trial database and the WCTU QA Team will be notified by the WCTU trial team. WCTU should be informed **within 24 hours** of any party becoming aware of the event.

Once received, the trial management team at WCTU will review the SAE. Information will be requested from the recruiting site to provide further detail on the SAE if required. If the patient was treated for the SAE at the investigator site that recruited the patient, WCTU will send the SAE on to the investigator site for completion within 2 working days (if not already reported by the site). If not then WCTU will contact the patient or the patients GP for further information where applicable.

For each **SAE** the following information will be collected from the intervention team, assessor and/or investigator site (as appropriate):

- details in medical terms and case description
- event duration (start and end dates, if applicable)
- action taken
- outcome

- seriousness criteria
- causality (i.e. relatedness to intervention), in the opinion of the investigator

The causality of SAEs (i.e. relationship to trial treatment) will be assessed by the site Principal Investigator and Chief Investigator(s) on the SAE form using Table 6.

Table 6 – SAE causal relationships

Relationship to trial intervention	Description
Unrelated	There is no evidence of any causal relationship
Unlikely to be related	There is little evidence to suggest there is a causal relationship (e.g. the event did not occur within a reasonable time after administration of the trial intervention e.g. within 48 hours). There is another reasonable explanation for the event (e.g. the participant's clinical condition, other concomitant treatment).
Possible relationship	There is some evidence to suggest a causal relationship (e.g. because the event occurs within a reasonable time after administration of the trial intervention). However, the influence of other factors may have contributed to the event (e.g. the participant's clinical condition, other concomitant treatments).
Probable relationship	There is evidence to suggest a causal relationship and the influence of other factors is unlikely.
Definitely related	There is clear evidence to suggest a causal relationship and other possible contributing factors can be ruled out.

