LIST OF FIGURES

Figure 1 – Trial Flow Diagram.....	16
Figure 2 – Gantt Chart of research timetable	45

TRIAL SUMMARY

Full Title	Remote multicomponent rehabilitation intervention in survivors of critical illness post hospital discharge: a randomised controlled assessor-blind clinical and cost effectiveness trial with internal pilot.
Short title	Remote Rehabilitation After Intensive Care (iRehab)
Duration of Trial	1 st January 2022 – 31 December 2024 (36 months)
Clinical Phase	Phase III
Trial Design	Pragmatic, randomised (allocation ratio 1: 1.17), controlled, assessor blind, multi-centre trial with internal pilot and embedded process evaluation.
Research question:	What is the clinical and cost effectiveness of a remote multicomponent rehabilitation intervention compared to standard care in survivors of critical illness following discharge from hospital after an Intensive Care Unit admission (ICU)
Trial Participants	Adults within 12 weeks of hospital discharge after treatment of a critical illness requiring ICU care and mechanical ventilation for ≥ 48 hours
Planned sample size	428 participants (197 control: 231 intervention) from at least 30 UK sites
Intervention	Six-week remote multi-component, individualised, rehabilitation intervention incorporating: weekly symptom management; targeted exercise; psychological support; and peer support and Information.
Control	Standard care offered at each site
Outcomes	
Measured pre-randomisation, eight weeks, six months post-randomisation
 
Primary: Health-related Quality of Life: EQ-5D-5L at eight weeks
 
Secondary: Physical Function: 30 second sit to stand test Illness Perception: Brief Illness perception questionnaire (BIPQ) Fatigue: Functional Assessment of Chronic Illness Therapy-Fatigue (FACIT-F) scale Anxiety and Depression: Hospital Anxiety and Depression Scale (HADS) Healthcare and social care utilisation Safety: Serious Adverse events Acceptability and Process Evaluation: Theoretical Framework of Acceptability Questionnaire

Follow-up	Remote follow up at eight weeks and six months (26 weeks)

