Week 6	Final 1-to-1 weekly session to include review and discharge	
 Encourage participant to continue with prescribed management plans Identify further sources of support Discharge from intervention.

There are four broad components to the iRehab intervention:

Component 1: Weekly focused discussion and expert guidance to determine individual symptoms and management plans

At each weekly appointment, participants will report any symptoms affecting their recovery, and an appropriate personalised management plan will be agreed. Standardised treatment strategies, individualised to the patient’s needs will be provided e.g. difficulty swallowing, breathlessness, fatigue, reduced appetite and other symptoms.

The intervention team member will help participants to set goals and incorporate the strategies for symptom management, exercise, and psychological wellbeing into an individualised action plan for the week ahead. Participants will continue with their individual rehabilitation techniques at home and progress will be reviewed and plans amended at the weekly appointments.

Component 2: Exercise and physical activity plans

At the first appointment (or as soon as possible), participants will be prescribed a progressive exercise and physical activity programme. This aims to address physical weakness, deconditioning and reduced function. Participants will work with the intervention team to agree goals and create action plans for their exercise and physical activity. Progression towards achieving these will be monitored and supported weekly, with discussion of strategies to overcome barriers (41, 58). Participants will be helped with their exercise/physical activity programme at the weekly appointments. They will be offered the use of a Fitbit (step counter) to help with the activity component if suitable. They will also be encouraged to complete an additional exercise session (either group based or individually).

Component 3: Psychological wellbeing support

At each weekly appointment participants will be supported to manage psychological symptoms e.g. anxiety or low mood, by undertaking a wellbeing activity, such as relaxation or a specific taught strategy. Symptoms will be assessed, and specific taught strategies or activities will be incorporated into the patient action plan. These will be reviewed weekly (59, 60).

Component 4: Group based peer support sessions and other information needs

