5.5 Hospital Readmissions

Investigator sites will be asked to report all hospital readmissions to the trial team via the eCRF. The trial team will use the date of the readmission to help determine, along with the investigator site, whether this constitutes an SAE.

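### The protocol gives conflicting observation periods for serious adverse events, and its reporting rule does not support the six-month SAE outcome that the Trial Summary lists

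*Protocol*

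**What the plan says.** The protocol addresses the SAE observation period in several places.

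- **Trial Summary, Outcomes.** The heading "Measured pre-randomisation, eight weeks, six months post-randomisation" stands over a list that includes "Safety: Serious Adverse events".
- **Section 1.5.2.** Objective (a) names adverse events and fixes them at eight weeks. Objective (b), on six-month effects, does not name them.
- **Section 2.2.2.** SAE collection is deferred to Section 4, which is Ethical Considerations; adverse events are in Section 5. The same section says that all measures are collected at baseline, eight weeks and six months.
- **Table 3 (Section 3.1).** AEs and SAEs are ticked at baseline, during the intervention, at week 8 and at week 26. The 8-26 week column is blank for both.
- **Section 5.2.1.** Recording and reporting run from consent to week 8 after randomisation, and in addition events "during the 8 week and 6-month outcome assessment appointments, must be recorded (AE)/reported (SAE) (where events are usually within 48 hours" of the appointment. The next paragraph says that at the baseline, eight-week and six-month assessments "all participants will be asked about anything that might constitute an AE or SAE by the independent assessor performing the assessment". That sentence gives no look-back period.
- **Section 5.5.** "Investigator sites will be asked to report all hospital readmissions to the trial team via the eCRF". The readmission date then helps the trial team and the site decide whether the event is an SAE.
- **Section 5.6.** All deaths are reported, whatever the cause and with no time limit stated.
- **Section 7.8.** In-patient contacts are collected over the six-month follow-up for the economic evaluation.

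**The concern.** A reader of the Trial Summary would expect a between-arm SAE comparison covering randomisation to six months. A reader of Section 5.2.1 would expect continuous reporting to week 8, then whatever surfaces around one appointment at week 26. These are different safety outcomes.

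The difference matters because exposure may not stop at week 8. At the final session (Table 1, week 6) the team is to "Encourage participant to continue with prescribed management plans", and those plans include exercise. A serious event at week 12 during continued home exercise falls outside the formal window. The causality rating in Section 5.2.1 and the notification to the ethics committee in Section 5.2.4 apply to SAEs, so an event not classed as one can miss both. An analysis plan could not repair this afterwards, because it cannot supply causality ratings that were never made or events that were never recorded.

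**Working it through.** The protocol states no figure for this window, so there is none to reproduce. The check is window arithmetic plus a comparison of the collection routes.

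**Inputs.** Continuous reporting ends at week 8 (Section 5.2.1). Follow-up ends at week 26 (Trial Summary). The usual look-back at an appointment is 48 hours, or 2 days (Section 5.2.1).

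**Length of the gap.**
- Week 8 = 8 × 7 = 56 days; week 26 = 26 × 7 = 182 days.
- Gap = 182 − 56 = 126 days (18 weeks), which is 126/182 = 69% of post-randomisation follow-up.

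**Share covered by the literal rule.**
- 48 hours before the six-month appointment: 2/126 = 1.6%, leaving 124 days (98.4% of the gap, 68% of follow-up) outside.
- Adding 48 hours after the eight-week appointment: 4/126 = 3.2%, leaving 122 days (96.8% of the gap, 67% of follow-up) outside.

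So about 97-98% of the gap is outside the formal SAE rule.

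**What the other routes add in weeks 8-26.**

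| Type of event | Collected? | Treated as an SAE with causality review? |
|---|---|---|
| Death | Yes (5.6) | Not stated for this interval |
| Hospital admission | Yes (5.5; in-patient contacts in 7.8) | Depends partly on its date (5.5) |
| Serious event without death or admission, such as persistent disability (5.1.2) | Only if raised by the open six-month question (5.2.1) | No clear rule |

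Section 5.5 does not say how the readmission date is to be used. The only SAE window in the protocol is that of Section 5.2.1, so the natural way to apply the date is against that window. On that reading a week-12 admission may be recorded as a readmission but not as an SAE. Nothing in the protocol says that readmissions or deaths enter a six-month serious-event comparison, and the in-patient data in Section 7.8 are there for costing.

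**The case against.** The strongest reply is that the safety objective is set at eight weeks and Section 5.2.1 governs. Section 1.5.2 ties adverse events to eight weeks, and the outcome list in Section 2.1 does not mention SAEs. The Trial Summary's heading on time points is generic: by Table 3 it is also inexact for the acceptability questionnaire (week 8 only) and for health and social care use (not at baseline). Table 3 can be read as agreeing with Section 5.2.1, with ticks at the appointments and a blank between. The 48-hour clause also has a plausible purpose. Section 5.2.4 covers harm from outcome assessments, and Table 6 uses 48 hours as an example of a reasonable interval for relatedness, so the week-26 tick may be aimed at harm from the assessment itself, such as the sit-to-stand test.

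Much of this stands. If it is the intention, however, the week-26 SAE entry is a check on assessment safety, and listing SAEs as a six-month outcome is wrong. The reply settles which way to reconcile the passages; it does not remove the conflict.

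A reader might infer that weeks 8-26 are almost unobserved, or that a six-month SAE table would show close to no events. The documents do not support either. Deaths and readmissions are reported without a week-8 cut-off, in-patient contacts are collected to six months, the six-month question is open, and the word for the 48-hour limit is usually, which is not absolute.

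**Conclusion.** The protocol is inconsistent on how long SAEs are observed. Under Section 5.2.1 read literally, 122-124 of the 126 days between weeks 8 and 26 fall outside SAE reporting, while the Trial Summary still lists SAEs at six months. A six-month SAE comparison on that basis would be incomplete and should not be presented as a cumulative 0-26 week count. Two specific gaps follow: later readmissions may be kept out of SAE status and causality review by their date, and serious events without death or admission have no clear rule in this interval.

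The percentages assume that 48 hours acts as a limit. If assessors take the open question back to week 8, coverage is better, but it then depends on each assessor's reading.

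I put no number on missed events. The protocol gives no event rate for weeks 8-26. The readmission figure in Section 1.1 (one in four within 90 days) runs from hospital discharge, whereas consent may come up to 12 weeks after discharge. Table 5 also exempts admissions and deaths for pre-existing conditions or complications of the initial ICU admission from SAE reporting even inside the window, so an assumed event rate would overstate the loss. The protocol specifies no six-month SAE table, so the consequence is conditional on one being produced.

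**What to change.** Reconcile the Trial Summary, Section 1.5.2, Section 2.2.2 (including its pointer to Section 4), Table 3 and Sections 5.2.1 and 5.5 on one SAE observation period. There are two coherent options.

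- **(a) Keep a six-month serious-event outcome.** Define it as all deaths and all hospital admissions from randomisation to week 26 in both arms, taken from the readmission eCRF, the death notifications and the resource-use data. Word the week-26 question to cover the whole period since the previous assessment. State in Section 5.5 how the readmission date is used. Send any event judged possibly related through Section 5.2.4 whatever its date.
- **(b) Limit SAEs to week 8.** Remove them from the six-month outcomes, say what the week-26 tick in Table 3 is for, and state that SAE conclusions apply to week 8 only.

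Option (b) costs a few lines of text. Option (a) costs the same wording, one reworded question and a few more SAE assessments after week 8; the death, readmission and in-patient data are already being collected.
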